8. SELECTION AND WITHDRAWAL OF SUBJECTS

8.1. Subject Inclusion Criteria

Visit 1 (Screening) and Visit 2 (Day 1), individuals of either gender or any race will be eligible for study participation if they:

1. Provide written informed consent and HIPAA authorization prior to any study-related procedures.
2. Are 18 years of age or older.
3. Are willing and able to follow instructions and can be present for the required study visits for the duration of the study, including:
 - a. Single-masked investigational product use compliance of at least 80% during the final week of Stage 1 [REDACTED]
[REDACTED]
 - b. [REDACTED]
[REDACTED]
4. Have a documented clinical diagnosis of dry eye disease in both eyes.
5. Have ongoing dry eye disease as defined by the following criteria in the **same eye or both eyes**:
 - a. Total corneal fluorescein staining (CFS) score [REDACTED] [National Eye Institute (NEI) scale] **at both Visit 1 (Screening) and Visit 2 (Day 1)** AND
 - b. [REDACTED] assessment of bulbar conjunctival hyperemia [REDACTED] [Cornea and Contact Lens Research Unit (CCLRU) scale] **at both Visit 1 (Screening) and Visit 2 (Day 1)** [REDACTED] AND
 - c. Unanesthetized Schirmer Test score of [REDACTED] **at Visit 1 (Screening)** in the same eye as qualified for 5b criterion above AND
 - d. [REDACTED] ocular discomfort severity (ODS) **at Visit 1 (Screening)** AND
 - e. [REDACTED] ODS score [REDACTED]
[REDACTED] AND
 - f. [REDACTED]
6. Have normal lid anatomy.

7. Are WOCBP who are not pregnant or lactating and not sexually active (i.e., abstinent) for 14 days prior to Visit 1 (Screening) and willing to remain so through 30 days following Visit 4 or the last administration of the investigational product or until completion of the subject's first menstrual cycle following the last administration of the investigational product, whichever period of time is longer. Alternatively, WOCBP who are not abstinent must have been using 1 of the following acceptable methods of birth control for the times specified:
 - a. IUD in place for at least **3 months** prior to Visit 1 (Screening) and continuing through Visit 4 or last administration of investigational product or until completion of the subject's first menstrual cycle following last administration of the investigational product, whichever period of time is longer.
 - b. Barrier method (condom or diaphragm) with spermicide for at least **3 months** prior to Visit 1 (Screening) and continuing through Visit 4 or last administration of the investigational product or until completion of the subject's first menstrual cycle following last administration of the investigational product, whichever period of time is longer.
 - c. Stable hormonal contraceptive for at least **3 months** prior to Visit 1 (Screening) and continuing through Visit 4 or last administration of the investigational product or until completion of the subject's first menstrual cycle following administration of the investigational product, whichever period of time is longer.
- NOTE: For Depo-Provera injection contraceptives, the statement regarding first menstrual cycle following administration of the investigational product is not applicable as females receiving this form of contraception will not have menses.
- d. In a monogamous relationship with a surgically sterilized (i.e., vasectomized) partner at least **6 months** prior to Visit 1 (Screening) through Visit 4 or last administration of the investigational product or until completion of the subject's first menstrual cycle following administration of the investigational product, whichever period of time is longer.
8. Are postmenopausal women (i.e., no menstrual cycle for at least one year prior to Visit 1 (Screening)) or are women who have undergone 1 of the following sterilization procedures at least 6 months prior to Visit 1 (Screening):
 - a. Bilateral tubal ligation
 - b. Hysterectomy
 - c. Hysterectomy with unilateral or bilateral oophorectomy.
 - d. Bilateral oophorectomy

8.2. Subject Exclusion Criteria

In order for subjects to be eligible at Visit 1 (Screening) and Visit 2 (Day 1) they may not:

1. Have a known hypersensitivity or contraindication to the investigational product(s) or their components.
2. Have used any of the following medications or had any of the following procedures within **30 days** prior to Visit 1 (Screening) or for the duration of the study:
 - a. Ocular, inhaled or intranasal corticosteroids
 - b. Ocular or oral non-steroidal anti-inflammatory drugs (NSAIDs) with the exception of ≤ 81 mg/day of acetylsalicylic acid (ASA or aspirin)
 - c. Topical ocular antibiotics
 - d. Topical ocular antihistamines or mast cell stabilizers
 - e. Oral antihistamines
 - f. Topical or nasal vasoconstrictors
 - g. Autologous serum tear preparations
 - h. Lipiflow treatment
 - i. TruTear treatment
 - j. Blephex treatment
3. Have used any of the following medications within **60 days** prior to Visit 1 (Screening) or for the duration of the study:
 - a. Topical cyclosporine (Restasis[®])
 - b. Topical lifitegrast
 - c. Any form of topical loteprednol etabonate (LE)
4. Have altered oral dosing of the following within **30 days** prior to Visit 1 (Screening) or anticipate alteration of dosing during the study:
 - a. Tetracycline compounds (e.g., tetracycline, doxycycline, or minocycline)
 - b. Omega-3 or Omega-6 supplements
5. Have altered dosing of the following medications within **6 months** prior to Visit 1 (Screening) or anticipate alteration of dosing during the study:
 - a. Anticholinergics
 - b. Anticonvulsants (e.g., topiramate)
 - c. Antidepressants

- d. Isotretinoin
- e. Systemic immunosuppressive agents including oral corticosteroids at a dose of prednisone \leq 11 mg/day or equivalent.

NOTE: Oral corticosteroid use at a dose of prednisone $>$ 11 mg/day or equivalent is excluded.

- 6. Be unwilling to abstain from the use of any topical ophthalmic medications **at Visit 1 (Screening)** and for the duration of the study, including:
 - a. Eyelash growth medications, including both prescription and over-the-counter
 - b. Eye drops, gels, ointments, or artificial tears
- 7. Be unwilling to abstain from the use TNF-blocking agents (e.g. etanercept, adalimumab, infliximab) **at Visit 1 (Screening)** and for the duration of the study.
- 8. Be currently receiving treatment for glaucoma **at Visit 1 (Screening)** or for the duration of the study and/or have history of or current glaucoma, or an IOP over 21mmHg **at Visit 1 (Screening) or Visit 2 (Day 1)**.
- 9. Be unwilling to abstain from wearing contact lenses for **14 days** prior to Visit 1 (Screening) and for the duration of the study.
- 10. Be monocular or have a BCVA of +1.0 logMAR or worse as assessed by Early Treatment Diabetic Retinopathy Study (ETDRS).
- 11. Have had penetrating intraocular surgery within **3 months** prior to Visit 1 (Screening) or anticipate requiring penetrating intraocular surgery during the study.
- 12. Have had corneal refractive surgery (e.g. Lasik) or corneal transplantation (full thickness, anterior or posterior).
- 13. Have had eyelid surgery within **6 months** prior to Visit 1 (Screening) or anticipate requiring eyelid surgery during the study.
- 14. Have congenitally absent lacrimal glands or meibomian glands.
- 15. Have had laser trabeculoplasty or anticipate requiring laser trabeculoplasty.
- 16. Have had cauterization of the punctum or have had punctal plugs (silicone or collagen) inserted or removed less than **3 months** prior to Visit 1 (Screening) or planned during the study.

NOTE: If subject starts the study with punctal plugs, they must remain in place for the duration of the study and must be replaced if inadvertently removed.

- 17. Have a diagnosis of:
 - a. Ongoing ocular infection
 - b. Moderate to severe pinguecula or pterygia

- c. Stevens-Johnson Syndrome
- d. Significant conjunctival scarring
- e. Significant anterior blepharitis
- f. Severe/serious ocular condition that in the judgment of the investigator could confound study assessments or limit compliance.
- g. Severe/serious systemic disease or uncontrolled medical condition that in the judgment of the investigator could confound study assessments or limit compliance.

18. Have Corneal Fluorescein Staining with diffuse confluent staining more than 33% of area (focal confluent staining is acceptable), or over 5 filaments or epithelial defects.

19. Have a history of herpetic keratitis.

20. [REDACTED]

[REDACTED]

[REDACTED]

[REDACTED]

[REDACTED]

21. Have a history of ocular allergies, which, in the judgment of the investigator, are likely to have an acute increase in severity due to the expected timing of exposure to the allergen to which the subject is sensitive. Subjects sensitive to seasonal allergens that are not expected to be present during the study are permitted.

22. Have been exposed to an investigational product within **30 days** prior to Visit 1 (Screening).

23. Be an employee of the practice that is involved in the management, administration, or support of this study or be an immediate family member of the same.

24. Have a documented history of alcohol and/or drug abuse.

25. In the opinion of the Investigator or study coordinator, be unwilling or unable to comply with the study protocol or unable to successfully instill eye drops.

26. Have used marijuana products for 72 hours prior to Visit 1 (Screening) and for the duration of the study.

27. Have been randomized for participation in KPI-121-C-006 (STRIDE 1) or KPI-121-C-007 (STRIDE 2).

8.3. Subject Withdrawal and Study Termination Criteria

Any subject who wishes to withdraw from the investigational product use or from participation in the study of his or her own accord for any reason is entitled to do so without obligation. The Investigator may also withdraw any subject from the investigational product use or from study participation, if deemed necessary.

Investigational product use may be discontinued and any subject may be discontinued from study participation at any time during the study at the discretion of the Investigator or the Sponsor for any reason including but not limited to:

1. Occurrence of any medical condition or circumstance that exposes the subject to substantial risk and/or does not allow the subject to adhere to the requirements of the protocol.
2. Any SAE, clinically significant AE, severe laboratory abnormality, intercurrent illness, or other medical condition that indicates to the Investigator that continued participation is not in the best interest of the subject.
3. Subject's decision to withdraw.
4. Any woman who becomes pregnant while participating in the study. Information on the pregnancy and outcome will be requested.
5. Subject's failure to comply with protocol requirements or study related procedures.
6. Termination of the study by the Sponsor, FDA, or other regulatory authorities.

In the event study discontinuation of a randomized subject is necessary, the Investigator should make every attempt to have subject complete Visit 4 assessments as possible. The reason for premature discontinuation should be entered onto the eCRF and recorded in the subject chart.

Subjects who withdraw from the study will not be replaced.

Additionally, the trial or parts of the trial may be discontinued by the Sponsor or at the recommendation of the Investigator after consultation with Kala Pharmaceuticals, Inc. This may be based on a significant number of AEs of a similar nature that warrant such action.

9. TREATMENT OF SUBJECTS

9.1. Description of Investigational product

The compositions of KPI-121 0.25% and its matching placebo (vehicle) are listed in Table 3 and Table 4, respectively.

TABLE 3: COMPOSITION OF KPI-121 0.25% (W/V) INVESTIGATIONAL PRODUCT

TABLE 4: COMPOSITION OF PLACEBO (VEHICLE)

Ingredient	Function	Concentration (% w/v)
Water	Vehicle	50
Hydroxyethylcellulose (HEC)	Thickener	2
Glutaraldehyde	Cross-linker	0.5
Ammonium Persulfate (APS)	Initiator	0.1
Tris(hydroxymethyl)aminomethane (Tris)	Neutralizer	0.1
Deionized Water	Vehicle	48

9.2. Concomitant Medications

All medications that the subject has taken 6 months prior to Visit 1 (Screening) and through Visit 4 or discontinuation from the study will be recorded in the eCRF and the subject chart. The generic name of the drug, dose, route of administration, duration of treatment (including start and stop dates), frequency, indication, and whether or not the medication was taken due to an AE or as a rescue medication will be recorded for each medication.

Medications and/or procedures not specifically excluded in the list below may be taken and/or conducted as necessary.

At **Visit 1 (Screening)** and for the duration of the study:

- Any topical ophthalmic medications including eyelash growth medications (including both prescription and over-the-counter), eye drops, gels, ointments, or artificial tears
- TNF-blocking agents (e.g. etanercept, adalimumab, infliximab)
- Treatment for glaucoma

Within **30 days** prior to Visit 1 (Screening) and for the duration of the study:

- Ocular, inhaled, or intranasal corticosteroids
- Ocular or oral non-steroidal anti-inflammatory drugs (NSAIDs) with the exception of ≤ 81 mg/day of acetylsalicylic acid (ASA or aspirin)
- Topical ocular antibiotics
- Topical ocular antihistamines or mast cell stabilizers
- Oral antihistamines
- Topical or nasal vasoconstrictors
- Other investigational products
- Autologous serum tear preparations

Within **60 days** prior to Visit 1 (Screening) and for the duration of the study:

- Topical cyclosporine (Restasis®)
- Topical lifitegrast
- Any form of topical LE

Within **30 days** prior to the screening visit (Visit 1) alteration to the dose or anticipated alterations to the dose of the following are disallowed:

- Tetracycline compounds (tetracycline, doxycycline, or minocycline)
- Omega-3 or Omega-6 supplements

Within **6 months** prior to the screening visit (Visit 1) alterations to the dose or anticipated alterations to the dose of the following are disallowed:

- Anticholinergics
- Anticonvulsants (e.g., topiramate)
- Antidepressants
- Isotretinoin

- Systemic immunosuppressive agents including oral corticosteroids at a dose of prednisone \leq 11 mg/day or equivalent.

NOTE: Oral corticosteroid use at a dose of prednisone $>$ 11 mg/day or equivalent is excluded.

Any subjects not responding adequately to the study medication may be rescued and placed on alternate therapy at the Investigator's discretion at any time. The choice of rescue medication is at the Investigator's discretion. Any subject placed on rescue therapy will discontinue use of the study medication and continue study participation through Visit 4.

The need for rescue therapy will not be considered an AE. Rescued subjects experiencing an AE at the time of rescue will be followed through stabilization or resolution of the AE or the end of the study (whichever comes last). Rescued subjects should not be withdrawn from the study, but rather followed to resolution of signs and symptoms or until the Investigator has deemed the subject is stable.

9.3. Treatment Compliance

Compliance will be assessed by [REDACTED] investigational product accountability records [REDACTED]. The site will document this [REDACTED] along with verification of the numbers of used and unused investigational product bottles. The numbers of missed doses as assessed at each clinic visit should be documented in the eCRF.

9.4. Randomization and Masking

The Sponsor, the project teams at the designated Contract Research Organizations (CROs), and investigative staff responsible for assessments of study endpoints will be masked to investigational product assignments. A dosing coordinator, who is not responsible for study assessments, will be required to dispense and retrieve investigational product to the subjects. In case of medical emergency, or occurrence of an SAE, the randomization code may be unmasked and made available to the Investigator, Sponsor, and/or other personnel involved in the monitoring or conduct of this study. In the absence of medical need, the randomization code will not be available to the above individuals until after the study is completed and the database is locked.

In the event of a medical need, the Investigator will treat each subject as needed. Since there is no specific antidote to KPI-121, immediate emergency unmasking is not necessary. If the Investigator feels it is necessary to unmask a subject's assignment after an emergency situation, the Investigator may call the medical monitor and notify the Sponsor. The investigational product assignment will be revealed on a subject-by-subject basis with the approval of the medical monitor and Sponsor, thus leaving the masking of the remaining subjects intact.

A randomization code will be computer-generated by Kala Pharmaceuticals, Inc. or designee. Randomization team members will work independently of other team members. Study personnel involved in subject assessment (i.e., not the dosing coordinator), study subjects, the Sponsor, and project teams at the CROs involved in the study will be masked to investigational product assignments.

10. INVESTIGATIONAL PRODUCT MATERIALS AND MANAGEMENT

10.1. Investigational product

KPI-121 0.25% ophthalmic suspension contains submicron particles of LE suspended in a formulation consisting of excipients that have been used in other FDA-approved ophthalmic products.

KPI-121 0.25% drug product will be supplied as a suspension in opaque dropper bottles. KPI-121 0.25% ophthalmic suspension is a sterile, aqueous, submicron suspension of LE and will be supplied in a 10 mL, white, low-density polyethylene dropper bottle with a translucent, controlled-drop linear low-density polyethylene tip, a pink high-density polyethylene cap, and a white, low-density polyethylene, tamper-evident overcap. Each bottle contains 8.2 mL (nominal fill) of drug product.

Subjects randomized to the vehicle control arm will receive the same bottles containing all components at the concentrations used in the KPI-121 0.25% ophthalmic suspension with the exception of the active component, LE.

10.2. Investigational product Packaging and Labeling

The Stage 1 investigational product will be 1 bottle of single-masked, investigational product (vehicle) from a common site level supply which will be provided to the subject after qualifying for Stage 1. The bottle labels for the single-masked period contain the following information: Sponsor name, protocol number, lot number, unique identifying number, storage temperature, and required statement(s) per the FDA requirements.

The randomized investigational product kit will consist of a box containing 2 dropper bottles of investigational product. At Day 1, eligible subjects will receive 1 bottle of investigational product. The second bottle will be retained at the site and provided to the subject in the event the subject needs additional investigational product during the treatment period. The box label and dropper bottle labels will contain the following information: Sponsor name, protocol and kit number, storage temperature, and required statement(s) per the FDA requirements.

10.3. Investigational product Storage

All investigational products will be stored at the site upright in a secure area, with limited access, at 15-25°C/59 -77°F.

10.4. Investigational product Preparation

Subjects will be instructed to shake the investigational product bottle for 2 to 3 seconds prior to each instillation.

10.5. Administration

At Visits 1 and 2, when subjects receive the first dose in the clinic, that dose will count as 1 of their 4 (QID) daily doses. Subjects will then self-administer at most 3 additional doses of investigational product during the remainder of that day to complete QID dosing. All visits should be scheduled in the morning to allow subjects to receive a full day of QID dosing. Any Stage 1 doses taken on the morning of Visit 2 should be counted into the total 4 doses for the day.

Subjects will be asked to instill 1 dose upon awakening and then 3 subsequent doses approximately 4 hours after their previous dose. The 4 doses will be described as “Morning Dose,” “Mid-Morning Dose,” “Afternoon Dose,” and “Evening Dose.”

10.6. Investigational product Accountability

Sponsor study monitors or designees will conduct accountability of investigational product (KPI-121 0.25% ophthalmic suspension or vehicle). Accountability will be ascertained by performing reconciliation between the amount of investigational product sent to the site and the amount used and unused at the time of reconciliation.

Clinical trial materials will be shipped to the investigational sites under sealed conditions. Investigational product shipment records will be verified by comparing the shipment inventory sheet to the actual quantity of investigational product received at the site. Accurate records of receipt and disposition of the investigational product (e.g., dates, quantity, subject number, dose dispensed, returned) must be maintained by the Investigator or his/her designee.

10.7. Investigational product Handling and Disposal

At the end of the study, all study materials, including any unused investigational products (KPI-121 0.25% ophthalmic suspension or vehicle), as well as original containers (even if empty), will be returned to the drug-packaging vendor in accordance with Sponsor or designee's Standard Operating Procedures (SOPs), following approval by the Sponsor. All returns of investigational product will be documented. The study monitor or designee will verify investigational product accountability. All investigational product accounting procedures must be completed before the study is considered complete.

11. ASSESSMENT OF EFFICACY

Efficacy assessments will be performed according to the schedule of events provided in Appendix 1 and include:

- Subject-rated assessment of ocular discomfort [REDACTED]
- [REDACTED] bulbar conjunctival hyperemia
- [REDACTED]
- [REDACTED] corneal fluorescein staining
- Subject-rated assessment of eye dryness

12. ASSESSMENT OF SAFETY

12.1. Safety Parameters

An ophthalmic examination will be performed at all study visits, except at Visit 3, according to the schedule of events provided in Appendix 1. Safety parameters include:

- Assessments of AEs
- BCVA
- Slit lamp biomicroscopy
- Dilated ophthalmoscopy
- IOP measurement
- Pregnancy screen (performed only at Visits 1 and 4 on WOCBP)*

*All pregnancies are to be reported from the time informed consent is signed until Visit 4/End of study. Any report of pregnancy for any subject must be reported within 24 hours of site awareness to Kala or its delegate using the Pregnancy Report Form. The Pregnancy form should be faxed to [REDACTED] or emailed to [REDACTED]

Women who have a positive pregnancy test during the study will be withdrawn from the study treatment and, whenever possible, should complete all remaining study visits and assessments. Every effort should be made to gather information regarding the pregnancy outcome and condition of the infant. It is the responsibility of the investigator to obtain this information within 30 calendar days after the initial notification and approximately 30 calendar days postpartum.

Pregnancy complications such as spontaneous abortion/miscarriage, premature birth or congenital abnormality are considered SAEs. The SAE must be entered on the AE eCRF in EDC and the SAE fax cover letter completed then faxed to 1-[REDACTED] or emailed to [REDACTED]

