7.4.4. Visit 4: Day 15 + 2 days – End of Study Visit

The end-of-investigational-product-use visit will occur on Day 15 +2 days as calculated from Visit 2: Day 1. The site staff will perform/assess the following in the order suggested below:

- Subject-rated assessment of eye dryness
- Use of any concomitant medications since the last visit
- Occurrence of any AEs since the last visit and a status review of any ongoing AEs
- [REDACTED]
- Used and unused double-masked investigational product collected, counted, and compliance assessed [REDACTED]
- [REDACTED] assessment of bulbar conjunctival hyperemia

- [REDACTED]
- BCVA
- Slit Lamp Biomicroscopy
- Corneal fluorescein staining
- IOP measurement
- Dilated ophthalmoscopy
- UPT for WOCBP
- Release of subject from the study

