12.4. Recording Adverse Events

AEs will be monitored throughout the study (from the time of ICF signature through Visit 4) and will be recorded on the eCRF with the date and time of onset, date and time of resolution, severity, seriousness, causality (relationship to use of investigational product), treatment required, and the outcome.

To elicit AEs, simple questions with minimal suggestions or implications should be used as the initial questions at all evaluation points during the trial. For example:

How have you felt since your last assessment?

Have you had any health problems since your last assessment?

The severity of each AE should be categorized as mild, moderate, or severe.

The causality of use of investigational product in relation to the AE will be assessed by the Principal Investigator after careful medical consideration and categorized as unrelated, unlikely, possible, probable, or definite.

If an AE occurs, the Investigator will institute support and/or treat as deemed appropriate. If a non-SAE is unresolved at the time of the last day of the study, an effort will be made to follow up until the AE is resolved or stabilized, the subject is lost to follow-up, or there is some other resolution of the event. The Investigator should make every attempt to follow SAEs to resolution.

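### Pregnancy reporting closes at Visit 4, the day of the last urine test, while contraception duties run later for most women of childbearing potential, so a Stage 2 conception recognised late may not be captured

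*Combined protocol and SAP*

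**What the plan says.** **Reporting.** Section 12.1 sets the window: "All pregnancies are to be reported from the time informed consent is signed until Visit 4/End of study". The next sentence is triggered differently and carries no end date: "Any report of pregnancy for any subject must be reported within 24 hours of site awareness". The section then asks for pregnancy outcome and infant condition, with follow-up to about 30 days postpartum, and classes pregnancy complications as serious adverse events (SAEs).

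**Testing.** Section 12.1 lists "Pregnancy screen (performed only at Visits 1 and 4 on WOCBP". Appendix 1 agrees. The early termination list in Section 7.4.6 also includes a urine test, but nothing is scheduled after a subject leaves.

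**Timing.** Section 7.4.4: "The end-of-investigational-product-use visit will occur on Day 15 +2 days as calculated from Visit 2: Day 1". That visit ends with release from the study.

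**Contraception.** Section 8.1, criterion 7, sets different end dates by group. Abstinent women must be "willing to remain so through 30 days following Visit 4 or the last administration of the investigational product", or until the first menstrual cycle is complete if that is later. IUD users have no 30-day term: "continuing through Visit 4 or last administration of investigational product or until completion of the subject's first menstrual cycle following last administration". The barrier, hormonal and vasectomized-partner options read similarly. For Depo-Provera users, "the statement regarding first menstrual cycle following administration of the investigational product is not applicable".

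**Related text.** Section 8.3 lists becoming pregnant during participation as a reason for discontinuation and says that pregnancy and outcome information will be requested. Section 12.4: "AEs will be monitored throughout the study (from the time of ICF signature through Visit 4".

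**The concern.** For most WOCBP the precautions against pregnancy outlast the period in which the protocol clearly asks for pregnancies to be reported. The reporting window also closes on the day of the last test, when the most recent conceptions are least likely to show.

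The obligations that matter for safety (outcome, infant condition, SAE classification of complications) begin only once a pregnancy is notified. If a woman conceives late in Stage 2, tests negative at Visit 4 and learns of the pregnancy afterwards, no visible step leads her to tell the site. A site that does hear could read Section 12.1 either way. Adverse event collection also stops at Visit 4, so it offers no second route.

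What is at stake is the completeness of the safety record for exposed pregnancies. Sample size, power and Type I error are not affected.

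**Working it through.** The plan gives no figure on this point, so there is none to reproduce. The check has two parts.

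**1. End dates side by side**

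| Rule | End date | Extension past Visit 4 |
|---|---|---|
| Reporting window (12.1) | Visit 4 / end of study | none |
| Report on site awareness (12.1) | not stated | open |
| Adverse event collection (12.4) | Visit 4 | none |
| Abstinent WOCBP (8.1, item 7) | later of 30 days after Visit 4 or last dose, and first menstrual cycle | at least 30 days |
| IUD, barrier, other hormonal, vasectomized partner (8.1, items 7a to 7d) | latest of Visit 4, last dose and first menstrual cycle | variable |
| Depo-Provera (note to item 7c) | Visit 4 or last dose | no cycle extension |

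The reporting window therefore ends before the contraception requirement for most WOCBP, by an amount that differs between groups.

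**2. What the Visit 4 test can see**

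Inputs:
- Stage 2 length T, from Section 7.4.4: 15 − 1 = 14 days to 17 − 1 = 16 days.
- Lag L from conception to a positive urine test: assumed, 6 to 14 days.
- Conception dates uniform over Stage 2: assumed.

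A conception in the last L days of Stage 2 is too recent to show at Visit 4. Share missed = min(1, L/T).

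| L (days) | T = 14 | T = 16 |
|---|---|---|
| 6 | 6/14 = 42.9% | 6/16 = 37.5% |
| 7 | 7/14 = 50.0% | 7/16 = 43.8% |
| 8 | 8/14 = 57.1% | 8/16 = 50.0% |
| 10 | 10/14 = 71.4% | 10/16 = 62.5% |
| 12 | 12/14 = 85.7% | 12/16 = 75.0% |
| 14 | 14/14 = 100% | 14/16 = 87.5% |

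The range is 37.5% to 100%. The share exceeds one half only when L > T/2, that is L > 7 days (T = 14) or L > 8 days (T = 16).

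**With the window moved.** At 30 days after Visit 4, every Stage 2 conception is at least 30 days old, beyond any lag in the assumed range. It could then be recognised and reported within the window. This does not guarantee capture, because reporting after Visit 4 would be passive.

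**The case against.** The best defence is that the Visit 4 cut-off is deliberate and coherent. It matches adverse event collection in a short trial, pregnancy is not among the safety summaries in Section 13.3, and the numbers will be small. This stands as a reason to rate the point low. It does not explain why Section 12.1 and criterion 7 use different end dates.

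Three stronger readings are tempting, and the documents do not support them.

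- *The plan's own risk window runs at least 30 days past reporting for everyone.* The 30-day term applies only to abstinent women. The other groups run to the first menstrual cycle, and Depo-Provera users have no cycle extension. The protocol never calls these periods a risk window; that is an inference from contraception criteria.
- *Late-recognised pregnancies are unreportable and would be lost.* The site-awareness sentence in 12.1 has no end date. Section 8.3 turns on becoming pregnant while participating, not on the date of discovery. Section 12.5 requires SAEs to be reported within 24 hours of coming to the site's attention, and that sentence has no end date either. A Stage 2 conception precedes Visit 4, so it can be read as falling inside the window. What remains is a conflict between this reading and the sentence that ends reporting at Visit 4.
- *Most Stage 2 conceptions would be missed.* This needs a test lag above 7 to 8 days, and the documents give no lag.

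It is also fair to say that an instruction to notify the site may exist out of sight. The consent pages were removed, some Visit 4 items are redacted, and Section 16.3 requires a 24-hour telephone number for medical concerns. The point is therefore that no such instruction is visible, not that none exists.

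**Conclusion.** The concern holds in a limited form, as a minor and inexpensive improvement. The reporting window in 12.1 ends on the day of the last urine test and before the contraception requirement for most WOCBP. Section 12.1 is ambiguous for a pregnancy conceived in Stage 2 and recognised after Visit 4, and no later ascertainment is visible.

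The 37.5% to 100% range describes what the Visit 4 test alone would fail to detect, and it depends wholly on the assumed lag and uniform conception dates. It is not an estimate of pregnancies permanently lost, since some would reach the site by other routes. The ambiguity and the mismatch of end dates do not depend on either assumption.

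**What to change.** Reconcile Section 8.1 criterion 7, Section 8.3 and Section 12.1:

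1. In 12.1, replace the Visit 4 cut-off with one reporting end-point for all WOCBP, no earlier than the longest post-treatment window in criterion 7. Because the menstrual-cycle term has no fixed date, say how the end-point is determined for each subject.
2. State that the rule covers pregnancies conceived on study and recognised after Visit 4, so that it agrees with the site-awareness sentence and with Section 8.3.
3. In Section 7.4.4, add an instruction that WOCBP notify the site of a pregnancy found within that period, and check that the consent form says the same.

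This concerns reporting only and takes no position on how long contraception should last.

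The cost is a few sentences in the protocol and possibly one in the consent form. Sites would accept passive reports for about a month after Visit 4. No visit, test, endpoint, sample size or significance level changes.
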